Primary Objective	To evaluate the safety of the SCD treatment up to seven consecutive 24 hour SCD treatments in the pediatric AKI population being treated with Continuous Renal Replacement Therapy (CVVH, CVVHD, or CVVHDF) with regional citrate anticoagulation.
Secondary Objective	To evaluate the effect of up to seven consecutive 24 hour SCD treatments on all cause mortality and dialysis dependency at day 28, and day 60 in the pediatric AKI population being treated with Continuous Renal Replacement Therapy (CVVH, CVVHD, or CVVHDF) with regional citrate anticoagulation. These outcomes will be compared to a historical data set.
Study Endpoints	In this Pilot study four domains of interest have been designated. The four domains are: 
 Patient Safety: Safety Endpoint Measures include adverse events, laboratory safety parameters, vital signs, EKG, ventilation status and hemodynamic variables. Clinical Efficacy: The Primary Clinical Efficacy Endpoint Measure is in-hospital; 28 and 60-day all-cause mortality. Time to renal recovery and necessity for chronic dialysis up to day 60 will also be determined. Additional efficacy endpoints include time to intensive care unit (ICU) discharge, and time to hospital discharge. Device Integrity and Performance: The Endpoint Measure is SCD use without failure. This measure will help assess the integrity and performance of the SCD device. SCD Mode of Action: Exploratory Endpoint Measures will include inflammatory cytokines, cell activation parameters and biomarkers at clinical sites with this capability.
Assessment of Device Integrity and Performance	Criteria for assessment of device integrity and performance include: 
 Significant Clotting within the Device as assessed by visual inspection. Evidence of leakage (i.e., cracking/breakage of a port, connector, hemofilter cartridge or tubing). Any unforeseen malfunction that results in the need for

	discontinuation.
Study Populations	Pediatric patients with a body weight (BW) greater than or equal to 15 kg receiving care in the Intensive Care Units of each participating hospital will be screened daily and identified for participation in the trial.
Study Design	This is an open-label, multi-center Pilot study.
Approximate Number of Subjects	Up to 30 patients will be enrolled in this study.
Approximate Number of Centers	Up to 10 Clinical Centers in the United States will participate in this study.

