	
17. Dry weight of <15 kg.18. Platelet count <15,000/mm³ at time of screening.19. Concurrent enrollment in another interventional clinical trial. Patients enrolled in clinical trials where only measurements and/or samples are taken (NO TEST DEVICE OR TEST DRUG USED) are allowed to participate.20. Use of any other Investigational drug or device within the previous 30 days.
Evaluation Plan	The primary evaluation of this study will be safety and all-cause mortality or dialysis dependency through 60 days post-enrollment. Additional endpoints will be time on CRRT, total ICU and hospital days. Mortality and dialysis dependency rates will be compared to historical controls.

LIST OF ABBREVIATIONS

[figure not shown]
AE	Adverse Event
AKI	Acute Kidney Injury
ARDS	Acute Respiratory Distress Syndrome
ARF	Acute Renal Failure
ATN	Acute Tubular Necrosis
BW	Body Weight
iCa	Ionized Calcium
CBC	Complete Blood Count
CRF	Case Report Form
CRRT	Continuous Renal Replacement Therapy
CTICU	Cardiothoracic Intensive Care Unit
CVVH	Continuous Veno-Venous Hemofiltration
CVVHD	Continuous Veno-Venous Hemodialysis
CVVHDF	Continuous Veno-Venous Hemodiafiltration
ECS	Extra Capillary Space
ICU	Intensive Care Unit
MICU	Medical Intensive Care Unit
nriCa	Non Recommended Ionized Calcium Range
ppCRRT	Prospective Pediatric CRRT Registry
PRISM	Pediatric Risk of Mortality
RAD	Renal Assist Device
riCa	Recommended Ionized Calcium Range
SAE	Serious Adverse Event
SCD	Selective Cytopheretic Device
SICU	Surgical Intensive Care Unit
SIRS	Systemic Inflammatory Response Syndrome
SOFA	Sequential Organ Failure Assessment
WBC	White Blood Cell
UADE	Unanticipated Adverse Device Effect

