2.4 PILOT STUDY USA ARF-002 - IDE [REDACTED]^[22]

2.4.1 STUDY SUMMARY

Acute kidney injury (AKI) is characterized by deterioration in kidney function resulting in multisystem abnormalities. Much of the morbidity and mortality associated with AKI result from a systemic inflammatory response syndrome (SIRS). This study described herein was a prospective, single-arm, multicenter US study designed to evaluate the safety and efficacy of the Selective Cytopheretic Device (SCD) treatment on AKI requiring continuous renal replacement therapy (CRRT) in the ICU. The study enrolled 35 subjects. The mean age was 56.3 ± 15 . With regard to race, 71.4% of the subjects were Caucasian, 22.9% were Black, and 5.7% were Hispanic. Average SOFA score was 11.3 ± 3.6 . Death from any cause at Day 60 was 31.4%. Renal recovery, defined as dialysis independence, was observed in all of the surviving subjects at Day 60. The results of this pilot study indicate the potential for a substantial improvement in patient outcomes over standard of care therapy, which is associated with a greater than 50% 60-day mortality in the literature. The SCD warrants further study in scientifically sound, pivotal trial to demonstrate reasonable assurance of safety and effectiveness.

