10. DATA SAFETY MONITORING BOARD

An independent Data Safety Monitoring Board (DSMB) will review safety results over the course of the study on a schedule set by CytoPherx, Inc. and the DSMB. The DSMB will comply with the FDA Guidance: “Guidance for Clinical Trial Sponsors on the Establishment and Operation of Clinical Trial Data Monitoring Committees”. The DSMB will be formed to provide scientific and medical feedback for the study.

The DSMB will focus on the following areas:

- *Performance* – to assess study conduct and compliance;
- *Effectiveness* – to assess mortality and dialysis dependency;
- *Safety* – to assess the incidence, severity, relationship, and timing of adverse events and to identify safety concerns; and
- *Context* – to assess the study relative to the AKI literature.

The DSMB will reflect the disciplines and medical specialties necessary to interpret the data from the clinical study and to fully evaluate participant safety. The SCD-PED-01 DSMB will be made up of at least 2 medical practitioners with expertise in AKI and critical care medicine. The DSMB will operate under a charter and will identify prospective data display specifications to conduct independent data reviews. The DSMB will make recommendations to the Sponsor to continue the study as planned or to stop the study due to safety. The DSMB will meet to perform safety evaluations and to provide feedback to the Sponsor at least annually as well as after 5, 10 and 16 of the cohort has completed 60 day follow-up. An efficacy evaluation to historical controls will be accomplished after all 16 enrolled patients have completed 60 day follow-up. The DSMB reserves the right to request more frequent evaluations.

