APPENDIX D – ENDPOINT DEFINITIONS

ALL-CAUSE MORTALITY:

All cause mortality is defined as in-hospital, 28-day and 60-day all cause mortality.

DIALYSIS DEPENDANCY AT DAY 60:

Dialysis dependency at day 60 is defined as patient not receiving any form of intermittent or continuous renal replacement therapy at or within 3 days of 60 days post enrollment in the study with no plans for additional intermittent or continuous renal replacement therapy.

PATIENT SAFETY:

Adverse events, laboratory safety parameters, vital signs, EKG, ventilation status and hemodynamic variables.

DURATION OF RENAL SUPPORT:

The duration of renal support will be defined as the numbers of days from the initiation of renal replacement therapy (start of observation period) to final dialysis treatment. Duration of renal support will be censored if the patient is still dialysis dependent at the time of death or are dependent at day 60.

RECOVERY OF RENAL FUNCTION:

Recovery of renal function will be defined as lack of need for continuous dialysis support on day 28, and will be classified as yes or no at day 28. Subjects who were alive at day 28 will be included in the analysis. Patients who remain dialysis dependent at study completion (day 60) or time of death will be categorized as having no recovery of renal function.

ASSESSMENT OF SCD █ INTEGRITY AND PERFORMANCE:

The SCD █ will be evaluated for the presence of clotting, leaking or any other malfunction.

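### Appendix D confines the day-28 renal recovery analysis to survivors and does not settle how a death before day 28 is scored

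*Combined protocol and SAP*

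**What the plan says.** Appendix D, under recovery of renal function, makes three statements:

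1. The definition: "Recovery of renal function will be defined as lack of need for continuous dialysis support on day 28", classified yes or no.
2. The analysis set: "Subjects who were alive at day 28 will be included in the analysis".
3. A rule for failures: "Patients who remain dialysis dependent at study completion (day 60) or time of death will be categorized as having no recovery of renal function".

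Section 3.2 lists mortality (in-hospital, 28-day and 60-day) as the primary clinical efficacy measure, adds time to renal recovery, and refers to Appendix D for definitions. The Evaluation Plan in the synopsis states: "The primary evaluation of this study will be safety and all-cause mortality or dialysis dependency through 60 days post-enrollment". It goes on: "Mortality and dialysis dependency rates will be compared to historical controls". The secondary objective in the synopsis and Section 3.1 both name dialysis dependency at day 28 as well as day 60, but Appendix D defines dialysis dependency only at day 60. Section 11 adds a 72-hour minimum of device treatment for entry to the final outcome analysis.

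**The concern.** The second and third statements do not fit together. Take a child who dies on dialysis on day 20. The second statement puts that child outside the analysis. The third, read at face value, makes the child a failure. The protocol does not say which governs, and in an open-label study the choice could be made after outcomes are known.

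Reconciling the two does not remove the problem. If the third statement is taken to cover only deaths between day 28 and day 60, the set is still day-28 survivors. Sections 1.1 and 11 state improved survival as the hypothesis, so membership of that set depends on an outcome the device is expected to alter. The recovery rate then moves with mortality as well as with kidney outcome. That matters most when it is placed beside historical controls whose mortality may differ.

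**Working it through.** The plan gives no expected recovery rate, test or sample size for this endpoint, so there is no design figure to reproduce. The check compares denominators.

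Notation: N = patients, D = deaths, R = survivors off dialysis.
- Survivors-only rate = R/(N − D)
- All-patient rate, deaths as non-recovery = R/N

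**Step 1. Earlier studies described in the protocol (adults, day 60).**

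ARF-002 (Section 2.4.1): N = 35 and mortality 31.4%, so D = 11 and 24 survived. On those survivors the protocol reports: "Renal recovery, defined as dialysis independence, was observed in all of the surviving subjects at Day 60". Hence R = 24.

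SCD-003, recommended-calcium subgroup with known outcome (Section 2.5.3, Tables 6, 8 and 9): 19 device patients with 3 deaths and 0/16 survivors dependent; 27 controls with 11 deaths and 4/16 survivors dependent. Hence R = 16 and R = 12. The tables agree with each other: 11 + 4 = 15, the control count in Table 9. The Pearson chi-square p-values reproduce: 0.0325 for Table 8 (stated 0.033) and 0.0065 for Table 9 (stated 0.007).

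| Group | Survivors only | Deaths as non-recovery |
|---|---|---|
| ARF-002 | 24/24 = 100% | 24/35 = 69% |
| SCD-003 device | 16/16 = 100% | 16/19 = 84% |
| SCD-003 control | 12/16 = 75% | 12/27 = 44% |

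The difference between the SCD-003 arms is 100 − 75 = 25 points among survivors and 84 − 44 = 40 points with deaths as failures. Survivors-only raised both rates and narrowed the difference.

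The 27 are not all in-range controls: 31 were in range, and three were lost to follow-up and one withdrew. Over all 31, the all-patient rate lies between 12/31 = 39% and 16/31 = 52%, depending on those four.

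**Step 2. Projection to this trial.** Assumptions: mortality m = 35% (from the registry's 65% survival in Section 11) or 50% (the upper figure in Section 1.1), both standing in for day-28 mortality; non-recovery n = 10–20% (Section 1.1), treated as a rate among survivors.

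- Survivors-only = 1 − n = 80–90%
- All enrolled = (1 − m)(1 − n)
- m = 35%: 0.65 × 0.80 = 52% to 0.65 × 0.90 = 58.5%; gap 28–31.5 points
- m = 50%: 0.50 × 0.80 = 40% to 0.50 × 0.90 = 45%; gap 40–45 points

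These rates do not depend on whether N is 16 or 30.

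**Step 3. Effect of the time-of-death sentence.** Suppose it covers every death. Let q be the share of deaths that are dialysis dependent, with the other deaths left out. With m = 35% and n = 15%, the rate is 0.65 × 0.85 / (0.65 + 0.35q):
- q = 0: 85%
- q = 0.5: 67%
- q = 1: 55%

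The reading of one sentence can therefore move the result by 30 points.

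**Step 4. Direction (hypothetical, N = 16).** With six deaths on dialysis and 8 of 10 survivors off dialysis, the rates are 8/10 = 80% and 8/16 = 50%. If two of those deaths become survivors still on dialysis, the survivors-only rate falls to 8/12 = 67% although more children live. The all-patient rate stays at 50%.

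**The case against.** Several counter-arguments have weight.

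- **The two sentences can be harmonised.** The set may be day-28 survivors, with the time-of-death clause covering only later deaths. That is possible, but the text does not say so, and the survivors-only set would remain.
- **A reader might infer that the recovery rate is simply inflated in the device's favour.** The documents do not support that. The rate is higher only relative to an all-enrolled denominator, and a survivors-only rate is a valid conditional estimate if labelled. In SCD-003 it reduced the advantage of the device.
- **A reader might infer that comparison with the registry is ruled out.** That is not shown. The yes/no recovery variable is not named for the historical comparison, the registry's definition of recovery is not given, and the same restriction could be applied to matched controls. What stands is that such a comparison is hard to interpret if mortality differs. Day-28 dialysis dependency is named for comparison, and this recovery definition is the only day-28 dialysis classification in Appendix D.
- **Deaths are counted elsewhere**, in the mortality measure and in the death-or-dialysis evaluation. This limits the consequences but leaves this endpoint's own rule open.
- **The evidence on size is indirect.** It comes from adults at day 60 and, for SCD-003, from a subgroup examined after the interim analysis. It shows that the gap can be large, not what it will be in children at day 28.
- **The pilot is small and unpowered.** The synopsis states "Up to 30 patients will be enrolled in this study", and Section 10 plans the historical comparison at a smaller number: "An efficacy evaluation to historical controls will be accomplished after all 16 enrolled patients". No test or decision rule rests on day-28 recovery. This lowers the severity.

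**Conclusion.** The concern holds as a defect of definition. Appendix D restricts day-28 recovery to survivors, and the adjoining sentence leaves the scoring of deaths before day 28 unsettled. The choice of denominator moved the rate by 16 to 31 points in the earlier studies (100 − 84 to 100 − 69 or 75 − 44). It would move it by about 28 to 45 points here, if mortality by day 28 is 35–50% and 10–20% of survivors do not recover. The effect on a comparison with controls has no fixed direction. Severity is moderate: this is a secondary endpoint in an unpowered pilot, and deaths enter the mortality and death-or-dialysis evaluations in any case.

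**What to change.** Replace the analysis-set sentence and the day-60/time-of-death sentence together. Changing only the first leaves a child who is off dialysis at day 28 but dependent later scored both ways. Suggested text:

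*Recovery at day 28 = alive and free of all renal replacement therapy at day 28, among all enrolled patients; death before day 28 counts as no recovery; status after day 28 does not change the day-28 classification.*

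The opening definition, which refers to continuous dialysis, should be brought into line with this text. In addition:

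- Report any survivors-only rate beside the all-enrolled rate, labelled as descriptive.
- Apply the same definition to registry controls if recovery or day-28 dialysis status is compared with them.
- State that the 72-hour exposure minimum in Section 11 does not remove early deaths from this denominator.
- Say how patients with unknown day-28 status (lost to follow-up or consent withdrawn) are shown.

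Settle this before the 16-patient evaluation. No new trial data are needed: renal replacement dates are recorded at the day-28 contact (Section 6.5.2), and deaths are captured as serious adverse events to day 60 (Sections 9.2 and 9.7.2). The cost is a short text change and a less favourable reported recovery rate.

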APPENDIX E – CRRT MANAGEMENT

Continuous Renal Replacement will be provided to all patients enrolled in the SCD-PED-01 Trial using automated equipment with integrated ultrafiltration control.

CRRT Modality:	Continuous
Blood Flow Rate:	Prescribed by Investigator Team – Treating Team
Dialysate Type:	Prescribed by Investigator Team – Treating Team
Dialysate Rate:	Prescribed by Investigator Team – Treating Team
Replacement Fluid Type:	Prescribed by Investigator Team – Treating Team
Ultrafiltration:	Prescribed by Investigator Team – Treating Team
Anticoagulation:	Regional Citrate Anticoagulation Only
Anticoagulation Prescription:	Prescribed by Investigator Team – Treating Team
CRRT Device	Gambro PrismaFlex, B. Braun Diapact
Hemofilter:*	Gambro Prismaflex HF 1000, Renaflow HF 400, Renaflow HF 700, Renaflow HF 1200
CRRT System Change:	Per participating center protocol
SCD █ Change:	Every 24 hours and as needed due to clotting
SCD Blood Tubing Set Change	With each SCD change
CRRT+SCD Interruption:	Up to twelve (12) hours per 24 hour period (or up to 24 hours if interruption was needed to initiate ECMO in the middle of the SCD course)

*Hemofilters can be provided to site by sponsor upon request. The clinical site will agree to use one of the protocol approved hemofilters for therapy.

APPENDIX F – SCD-PED-01 Study Schedule of Events

	Baseline	Hr 0-24	Hr 25-48	Hr 49-72	Hr 73-96	Hr 97-120	Hr 121-144	Hr 145-168	Therapy End
Vital Signs/Physical Assessment									
Temperature , Body Weight (baseline only)	X	X	X	X	X	X	X	X	
Blood Pressure (if no bp, MAP acceptable), Heart Rate	X	X	X	X	X	X	X	X	
PRISM II Score	X								
Physical Exam	X								
Urine Output (previous 24 hours)	X	X	X	X	X	X	X	X	
Net Fluid Balance (previous 24 hours)		X	X	X	X	X	X	X	
Sepsis	X								
ICU Percent Fluid Overload at CRRT Initiation	X								
Clinical Laboratory Testing									
CBC with differential	X	q12h	q12h	q12h	q12h	q12h	q12h	q12h	
BUN/Creatinine	X	X	X	X	X	X	X	X	
Na, K, Cl, HCO ₃ , Ca, Mg, PO ₄ , Ionized Calcium	X	X	X	X	X	X	X	X	
ALT, AST, Bilirubin, ALP, TP, Albumin, Glucose	X	X	X	X	X	X	X	X	
PT, PTT, INR	X	X	X	X	X	X	X	X	
Urinalysis (if urine is available)	X								
Respiratory									
Arterial Blood Gas (pH, PaO ₂ , PaCO ₂) (if on vent)*	X	X	X	X	X	X	X	X	
Ventilator Settings (FiO ₂)	X	X	X	X	X	X	X	X	
Blood For Research									
Blood for Biomarkers	X		X(hr/48)		X(hr/96)		X(hr/144)		X
Extracorporeal Device Parameters									
CRRT (Settings- Event Driven)	X (hour 0)	X	X	X	X	X	X	X	
Post Filter Ionized Calcium	X (hour 0)	q1h until <0.40mmol/L; then q6h	q6h	q6h	q6h	q6h	q6h	q6h	
CRRT Device and SCD Performance (Event Driven)		X	X	X	X	X	X	X	
SCD 24hr. Daily Change		X	X	X	X	X	X	X	
Other (Event-Driven)									
Adverse Events	X	X	X	X	X	X	X	X	X
Critical Medications, Blood products (yes/no) per Appendix J	X	X	X	X	X	X	X	X	X
Diagnosis/Therapeutic Procedures	X	X	X	X	X	X	X	X	X
Microbiology/culture data	X	X	X	X	X	X	X	X	

*Required only if the presence of an A-line; see **Section 6.3** and **Section 6.4** for details

APPENDIX G – SCD-PED-01 Study Schedule of Events: Follow-up Period**Day 1 - 5 or until ICU discharge (whichever occurs first unless otherwise specified)**

Measurement	Hour 0 - 24	Hours 25 – 120 ¹
Vital Signs/Physical Assessment		
Blood pressure, temperature, and heart rate	X	X
Physical Exam	X	
Urine Output (from previous 24 hours)	X	X
Net Fluid Balance – (from previous 24 hours)	X	X
Clinical Laboratory Tests		
CBC with differential	X	
BUN/Creatinine	X	
Na, K, Cl, HCO ₃ , Ca, Mg, PO ₄ , Ionized Calcium	X	
Respiratory:		
Arterial Blood Gas (pH, PaO ₂ , PaCO ₂)	X	
Ventilator Settings (FiO ₂)	X	X
Other(event driven)		
Renal Replacement Therapy status	X	X
Microbiology/Culture Data	X	X
Adverse Events	X	X
Serious Adverse Event	X	X
Antibacterial Medications (yes/no)	X	X

¹Events listed in this column are to be performed once per 24 hour time period.

APPENDIX H – SCD-PED-01 Study Schedule of Events: Day 28 and Day 60

Measurement	Day 28 ¹	Day 60 ²
Presence of mechanical ventilation (since last visit)	X	X
Presence of renal replacement therapy (since last visit)	X	X
Hospital and ICU Discharge information	X	X
Serious Adverse events (since last visit)	X	X
Serum Creatinine (if office visit takes place)	X	X

¹ This visit may be done via telephone call or office visit. Please record the above information on day 28 (+7 days) following enrollment.

² This visit may be done via telephone call or office visit. Please record the above information on day 60 (+7 days) following enrollment.

APPENDIX J – CRITICAL MEDICATION LIST

The following is a list of medication categories (with examples) to be acknowledged (yes/no) in the Case Report Forms if administered to the patient during the SCD-PED-01 Clinical Trial (starting at 24 hours prior to Observation until 168 hours of treatment or ICU discharge, whichever comes first. Only antibacterial use is captured during follow-up period.

ANTIBACTERIALS FOR SYSTEMIC USE

Ampicillin	Ceftazidime	Moxifloxacin
Azithromycin	Ciprofloxacin	Nafcillin
Aztreonam	Ciprofloxacin hydrochloride	Piperacillin
Bactrim (Sulfamethoxazole, Trimethoprim)	Clindamycin	Piperacillin w/tazobactam (Piperacillin, Tazobactam)
Cefadroxil	Daptomycin	Synercid (Dalfopristin,Quinupristin)
Cefalexin	Doripenem	Tigecycline
Cefazolin	Erythromycin	Tobramycin
Cefazolin sodium	Gentamicin	Vancomycin
Cefepime	Levofloxacin	
Cefepime hydrochloride	Linezolid	
Cefoxitin	Meropenem	
	Metronidazole	

ANTIMYCOTICS FOR SYSTEMIC USE

Amphotericin b, liposome	Fluconazole
Caspofungin	Micafungin

ANTITHROMBOTIC AGENTS

Acetylsalicylic acid	Clopidogrel	Enoxaparin sodium
Argatroban	Drotrecogin alfa	Heparin
Bivalirudin	Enoxaparin	Warfarin sodium

BLOOD SUBSTITUTES

Albumin	Albumin human	Blood, whole
Cryoprecipitate	Red blood cells	
Plasma	Red blood cells, leucocyte depleted	
Platelets		

VASOPRESSORS

Dobutamine	Norepinephrine	Phenylephrine hydrochloride
Dopamine	Norepinephrine bitartrate	Vasopressin
Epinephrine	Phenylephrine	
Milrinone		

APPENDIX K – CRRT PRESCRIPTION GUIDELINE and REGIONAL CITRATE ANTICOAGULATION (RCA) PROTOCOL EXAMPLE

1. **Purpose:** The purpose of the guidelines is to standardize, to the extent possible, the provision of CRRT to patients who require CRRT. While these guidelines should govern the CRRT prescription provided to most patients, there will be special circumstances (e.g. inborn errors of metabolism, exogenous toxin removal) that will require deviation from these guidelines.
2. **Modality:** CRRT will be prescribed as continuous veno-venous hemodiafiltration (CVVHDF). A total minimum small solute clearance of 2000 ml/min/1.73m² will be prescribed. The clearance will be divided equally between dialysis and hemofiltration as follows:
 - a. 50% as dialysis fluid using PrismaSateTM via the dialysis pump
 - b. 50% as replacement fluid divided between pre-replacement and post-replacement as follows:
 - i. 50 ml/hour as post-filter replacement fluid via the replacement fluid pump using (PrismaSolTM). This is necessary to prevent clotting of the deaeration chamber (50 ml/hour is the lowest allowable rate)
 - ii. The remaining fluid rate (total replacement fluid rate – 50 ml/hour) pre-filter replacement fluid via the pre-blood pump (PBP) using PrismaSolTM.
 - c. The composition of PrismaSateTM and PrismaSolTM should be equivalent. Any additives (e.g. potassium chloride) should be added in equivalent concentrations to both dialysis and replacement solutions.

3. Regional citrate anticoagulation: All CRRT circuits will receive regional citrate anticoagulation. The initial prescription and calcium level monitoring will be based on the size of patients and the presence, or lack thereof, of significant hepatic dysfunction. **REMEMBER TO ACCOUNT FOR THESE FLUIDS IN THE PATIENT REMOVAL RATE AS THESE ARE EXTERNAL TO THE CRRT MACHINE.**

a. Patients > 1 year of age and with normal hepatic function:

- i. Order ACD-A™ and CaCl₂ (8 grams/1 liter NS) to bedside
- ii. Initial ACD-A™ rate = 1.5 x CRRT blood pump rate x min/hour (e.g., if blood pump rate is 100 ml/minute; the ACD-A™ rate is 150 ml/hour). This is to be infused at a stopcock or y-connector on access line.
- iii. Initial CaCl₂ rate = 0.6 x blood pump rate x min/hour (e.g., if blood pump rate is 100 ml/minute; the CaCl₂ rate is 60 ml/hour).
- iv. Calcium monitoring schedule
 1. Check patient total and ionized calcium prior to CRRT initiation.
 2. Check patient and system ionized calcium 5 minutes after CRRT settings at prescribed rates.
 3. Check patient and system ionized calcium 2 hours after CRRT settings at prescribed rates.
 4. Check patient and system ionized calcium every 8 hours thereafter
 5. Check patient total calcium daily
 6. Check patient and system ionized calcium one hour after any change in ACD-A™ or CaCl₂ rate

b. Desired Calcium Concentration ranges

- i. Circuit ionized calcium = 0.25 to 0.40 mmol/L
- ii. Patient ionized calcium = 1.1 to 1.3 mmol/L (a higher level may be requested by ICU/CICU service if clinically indicated)
- iii. Patient systemic calcium = 8 to 12 mg/dL

c. Citrate anticoagulation management

- i. Bedside RN to call for patient ionCa < 1 mmol/L or > 1.5 mmol/L, or circuit ionCa < 0.25 mmol/L or > 0.40 mmol/L
- ii. Circuit ionCa managed with ACD-A™ rate
 1. For circuit ionCa < 0.25 mmol/L, decrease ACD-A™ 10%
 2. For circuit ionCa > 0.40 mmol/L, increase ACD-A™ 10%
- iii. Patient ionCa managed by CaCl₂ rate
 1. For patient ionCa < 0.9, increase CaCl₂ 20%
 2. For patient ionCa 0.9- 1, increase CaCl₂ 10%

3. For patient ion Ca 1.3-1.5, decrease CaCl₂ 10%
4. For patient ion Ca > 1.5, decrease CaCl₂ 20%

- 4. Access Size: (per clinical investigator decision)**
- 5. Blood pump flow rate: The minimum blood pump flow rate should be 50 ml/minute to prevent circuit clotting unless not clinically tolerated:**
 - a. Neonate/Infants – 8 to 12 ml/kg/minute
 - b. Toddlers – 6 to 8 ml/kg/minute
 - c. Older children and adolescents – 3-6 ml/kg/minute
- 6. 3-hour Fluid Balance Safety Limit: Limits set to prevent < 5% of blood volume error over 3 hours for smaller patients and < 10% over three hours for larger patients**
 - a. Patients < 30 kg – 150 ml
 - b. Patients 30-50 kg – 200 ml
 - c. Patients > 50 kg – 300 ml
- 7. Scheduled circuit changes: Circuits should be changed no later than every 72 hours, as this is the maximum interval at which the machine has been tested by the manufacturer for accuracy. Any diversion from this recommendation must have rationale documented in the medical record. The following situations serve as examples:**
 - a. The patient has a do not resuscitate or do not escalate care order that was placed on the chart while the patient is receiving CRRT.
 - b. The patient is so clinically unstable that the patient will likely not tolerate stopping and restarting CRRT.
- 8. Blood priming at CRRT initiation and blood return at CRRT termination**
 - a. Blood priming of the CRRT circuit should be done if the extracorporeal volume of the circuit is > 10% of the patient's blood volume.
 - b. Blood should not be returned to the patient at CRRT termination when circuits are blood primed unless specifically requested by the physician in a separate order.

